affected by HIV. The majority of HIV infections among MSM occur through exposure to the rectal mucosa during condomless receptive anal intercourse (CRAI), and among women through exposure to the vaginal mucosa regions, within the female genital tract, during condomless vaginal intercourse. To aid in prevention, pre-exposure prophylaxis (PrEP) and post-exposure prophylaxis (PEP) are recommended for HIV exposure. Current CDC recommendations for PrEP is to take the combination anti-HIV drug, tenofovir+emtricitabine (TDF/FTC or TAF/FTC), on a daily basis for the duration of someone's HIV risk exposure period, which could be months or years. For PEP, a three-drug anti-HIV medication is recommended within 72 hours of a possible exposure, for a 28-day course, according to the CDC. While PrEP and PEP are efficacious, both the daily dosing of PrEP and the 28-day course of PEP limit their utility in practice, as many users find long term adherence to these regimens to be difficult. Therefore, short course regimens taken around the time of sex (On-demand or Event-Driven PrEP; ED-PrEP) are appealing to some, and WHO endorses one such ED-PrEP regimen for MSM: two doses of TDF/FTC between 2 and 24 hours before sex, one dose 24 hours after sex, and another dose 48 hours after sex. Although short course regimens have been proven to reduce one's risk of HIV infection, interventions for STI prevention have yet to be approved for use. Recent studies have shown a single dose of oral doxycycline (DOX) taken within 24 hours after having sex, can protect against STIs among MSM. A multi-purpose dosing strategy that combines DOX with ARVs could allow for a single event-driven oral dosing combination to be taken after sex for protection against HIV and other STI infections. The aim of this study is to better understand the ability of DOX, TAF, FTC, & bictegravir (BIC) to penetrate mucosal tissues after a single oral dose, and to examine how well the tissues retain protective drug levels over an extended period of time in both men and women.

4. Study Endpoints

Primary Endpoint: to compare doxycycline concentrations in rectal and vaginal biopsies collected 24 hours after a single dose.

Secondary Endpoint: The comparison of bictegravir concentrations in rectal and vaginal biopsies collected 24 hours after a single dose.

5. Study Intervention/Investigational Agent

Doxycycline

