Visit 6 (24 hours post-dose): Approximately 18 mL of blood will be drawn. If the participant has a penis, one urethral swab and one glans swab will be collected. If the participant has a vagina, a vaginal swab will be collected. A urine sample will then be collected from all participants.

Participants who have a vagina will undergo a vaginal/cervical biopsy. All other participants will undergo a rectal biopsy. Participants who complete the vaginal biopsy will have the **option** to also undergo the rectal biopsy at Visit 6. Once the scope (rectal) or the speculum (vaginal) is inserted, additional swabs will be inserted in the rectum or vagina to collect secretions. Then, up to 12 rectal biopsies, or 1 to 2 vaginal and 1 to 2 cervical biopsies will be collected. All participants will be informed not to place anything into the rectum or vagina and abstain from intercourse for 7 days after their biopsy procedure(s) to allow the mucosa to heal.

Vaginal and cervical tissue samples will not be collected in women who are menstruating, pregnant, or have possible cervical or vaginal infection. A pregnancy test will be administered to women of childbearing potential to ensure they are not pregnant. Visit 2 will also be scheduled 7 to 10 days after their last menstrual cycle.

Visit 7 (48 hours post-dose): Approximately 18 mL of blood will be drawn. Then participants will provide a urine sample and self- collect rectal or vaginal fluid swab samples.

Visit 8 (72 hours post-dose): Approximately 18 mL of blood will be drawn. Then participants will provide a urine sample and self- collect rectal or vaginal fluid swab samples.

Visit 9 (96 hours post-dose): Approximately 18 mL of blood will be drawn. Then participants will provide a urine sample and self- collect rectal or vaginal fluid swab samples.

Visit 10 (7 days post-dose): Approximately 18 mL of blood will be drawn. Then participants will provide a urine sample and self- collect rectal or vaginal fluid swab samples.

Timing of procedures after dose: The procedures conducted after dose, particularly those less than 24 hours after dose, should occur as close to the scheduled time points as possible. Protocol deviations will be not filed for visits that occur outside of the target windows but will be noted in source documents.

Contingency visit: If needed, participants may be brought in for additional study visits. This would occur if, for example, screening laboratory results are lost or are inconclusive.

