Primary Outcomes: Comparison of doxycycline concentrations in blood and tissue between men and women. Plasma doxycycline concentrations at 24 hours will be compared between men and women using a Wilcoxon test. Median rectal and vaginal swab doxycycline concentrations collected at 24 hours after dosing will be compared using a Wilcoxon test. Median rectal and cervical tissues doxycycline concentrations collected at 24 hours after dosing will be compared using a Wilcoxon test. P-values less than 0.05 will be considered significant.

Exploratory Outcomes: Comparison of TAF, FTC, and BIC concentrations in blood and tissue between men and women. Plasma TAF, FTC, and BIC concentrations at 24 hours will be compared between men and women using a Wilcoxon test. Median rectal and vaginal swab TAF, FTC, and BIC concentrations collected at 24 hours after dosing will be compared using a Wilcoxon test. Median rectal and cervical tissue TAF, FTC, and BIC concentrations collected at 24 hours after dosing will be compared using a Wilcoxon test. P-values less than 0.05 will be considered significant.

19. Provisions to Monitor the Data to Ensure the Safety of Participants

Adverse Events

An Adverse Event (AE) as any untoward medical occurrence in a clinical investigation subject administered a pharmaceutical product regardless of its causal relationship to the study treatment. An AE can therefore be any unfavorable and unintended sign (including an abnormal laboratory finding), symptom or disease temporally associated with the use of a medicinal (investigational) product.

Any AE that is reported to either the investigators or their designated research associates by a study subject or by medical staff caring for the subject and which meets the criteria will be documented in the participant's chart. The reporting period for participant AEs begins at enrollment (Visit 2) and continues until the subject either completes or withdraws from the study.

All AEs and laboratory abnormalities will be graded according to the Division of AIDS Table for Grading the Severity of Adult and Pediatric Adverse Events (DAIDS AE Grading Table), Version

2.1, July 2017, which can be found on the DAIDS RCC Web site: http://rcc.tech-res.com/tox_tables.htm.

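### The primary endpoint names vaginal biopsies, but the SAP tests only cervical tissue against rectal; the same tests also vary body site and sex together

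*Combined protocol and SAP*

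**What the plan says.** **Endpoints (Section 4).** The primary endpoint is "to compare doxycycline concentrations in rectal and vaginal biopsies collected 24 hours after a single dose". The secondary endpoint is "The comparison of bictegravir concentrations in rectal and vaginal biopsies collected 24 hours after a single dose". Both are framed by body site, and both name vaginal tissue.

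**Analysis (Section 18, Statistical Analysis Plan).** The primary outcomes are headed "Comparison of doxycycline concentrations in blood and tissue between men and women", so here the contrast is framed by sex. Three doxycycline tests follow: plasma in men versus women; swabs, "Median rectal and vaginal swab doxycycline concentrations collected at 24 hours after dosing will be compared using a Wilcoxon test"; and tissue, "Median rectal and cervical tissues doxycycline concentrations collected at 24 hours after dosing will be compared using a Wilcoxon test". For the antiretrovirals, listed as exploratory outcomes, the tissue test is "Median rectal and cervical tissue TAF, FTC, and BIC concentrations collected at 24 hours after dosing will be compared using a Wilcoxon test". No test of vaginal tissue appears for any drug.

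**Collection (Section 6, Visit 6, 24 hours).** "Participants who have a vagina will undergo a vaginal/cervical biopsy. All other participants will undergo a rectal biopsy". In the vaginal/cervical procedure, "1 to 2 vaginal and 1 to 2 cervical biopsies will be collected". Further swabs are taken in whichever organ is being scoped or examined. Women may also choose a rectal biopsy (study summary table and Visit 6), which is paid for separately (Section 17). Section 18 does not mention these optional samples.

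**The concern.** The tissue in the primary endpoint and the tissue in the primary analysis differ, and so do the tissue and the status (secondary or exploratory) given to bictegravir. Someone following Section 18 would report a primary result that does not address Section 4. Someone following Section 4 would have to add a test that was not prespecified. While both readings stand, the choice between vaginal and cervical tissue can be made after the results are known.

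The second issue is interpretation. Rectal specimens come mainly from men and female-tract specimens from women. Section 4 invites the reader to see a site difference and Section 18 a sex difference, and one unpaired test cannot say which it is. Women's optional rectal biopsies are the only planned tissue that could help separate the two. Section 18 gives them no analysis and does not say whether they count as rectal samples in the main test.

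**Working it through.** **1. Endpoint against analysis**

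| Item | Section 4 | Section 18 SAP | Collected at Visit 6? |
|---|---|---|---|
| Doxycycline, female-tract tissue | vaginal (primary) | cervical (primary) | both |
| Bictegravir, female-tract tissue | vaginal (secondary) | cervical (exploratory) | both |
| Rectal tissue | yes | yes | yes |
| Vaginal swab | not an endpoint | tested | yes |

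The vaginal swab test does not fill the gap, because Section 4 specifies biopsies. The missing element is vaginal tissue, and it is available for analysis.

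**2. What the mismatch could do**

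The documents give no SD, effect size or power, so 20 participants (10 women, 10 MSM) cannot be re-derived and is not disputed here. For scale only, assume:
- lognormal concentrations with total CV 30%, 51% or 80%, so log-SD = √ln(1+CV²) = 0.294, 0.481 or 0.703;
- a two-sided exact rank-sum test, 10 v 10, rejecting at U ≤ 23 (actual size 0.043). Section 18 states neither sidedness nor which Wilcoxon test is meant.

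Suppose rectal and vaginal concentrations are equal and cervical differs from vaginal 1.5-fold. The standardised difference is ln 1.5 / SD = 0.405/0.294, 0.405/0.481 and 0.405/0.703, that is 1.38, 0.84 and 0.58. By simulation (40,000 runs) the cervical test rejects in about 79%, 39% and 20% of trials. On the endpoint as stated there is no difference to find.

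**3. Site and sex together**

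On the ratio scale the raw contrast factorises:

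rectal men / female-tract women = (rectal men / rectal women) × (rectal women / female-tract women).

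The first factor is sex at a fixed site and the second is site within women. The unpaired test sees only the product. The same power figures apply if there is no site effect and women's tissue is 1.5 times men's: about 79%, 39% and 20%. Those are correct rejections for the raw concentrations, and wrong only if reported as a site effect. If a 1.5-fold site ratio and an opposing 1.5-fold sex ratio cancel exactly, the test rejects at about its size, 4%.

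The 24-hour swab test has the same structure. Table 1 lists no self-collected swabs at Visit 6, so rectal secretions at 24 hours come from the scope procedure.

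**4. If optional rectal samples were pooled as independent**

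Let k women contribute to both groups, with within-woman correlation 0.5 and no true difference. A nominal 0.05 rank-sum test then has size 0.028 at k = 5 and 0.019 at k = 10. Ignoring the pairing makes the test conservative, and who is in the rectal group changes with uptake.

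**5. What the within-woman comparison can deliver**

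The 95% CI factor for the rectal/female-tract geometric mean ratio is exp(t₀.₉₇₅,ₖ₋₁ × SD × √(2(1−ρ)/k)). With ρ = 0.5 this is exp(t × SD/√k). For k = 3 at CV 51%: exp(4.303 × 0.481/1.732) = 3.3.

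| Pairs | CV 30% | CV 51% | CV 80% |
|---|---|---|---|
| 3 | ×/÷ 2.1 | ×/÷ 3.3 | ×/÷ 5.7 |
| 5 | ×/÷ 1.4 | ×/÷ 1.8 | ×/÷ 2.4 |
| 8 | ×/÷ 1.3 | ×/÷ 1.5 | ×/÷ 1.8 |

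For reference, an unpaired 10 v 10 comparison gives ×/÷ 1.3, 1.6 and 1.9. The smallest two-sided signed-rank p is 2/2⁵ = 0.0625 with five pairs and 2/2⁶ = 0.031 with six, so with five or fewer pairs that test cannot reach 0.05.

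**The case against.** The strongest defence concerns the confounding. The study asks how drug distributes in mucosal tissue, and Section 3 explains that MSM are exposed mostly through the rectum and women through the vagina. Comparing each group at its own exposure site follows from that, and Section 18 openly heads the comparison as men versus women. Nowhere do the documents attribute a difference to site alone. This stands. The raw test is valid for what it compares, and the rejection rates in step 3 are power under assumed variances, not error rates. A reader might infer that the planned tests are invalid or have an inflated false-positive rate, but the documents do not support that.

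On the optional biopsies, uptake is unstated, the women who accept are self-selected, and three pairs give a very wide interval. Describing such data without a test is reasonable in a 20-person study. This also stands, and it limits the remedy to estimation.

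Neither argument answers the vaginal/cervical contradiction. The study's small size is no answer either, because Section 18 calls these primary outcomes and applies a 0.05 threshold to them.

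A reader might also go too far here and infer that nothing named in the primary endpoint is tested. Rectal tissue is tested; the gap is vaginal tissue alone.

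**Conclusion.** Section 18 is wrong as written against Section 4. The stated primary comparison (doxycycline, rectal versus vaginal biopsy) and the matching bictegravir secondary comparison have no test, although the tissue is collected. This rests on the text alone. How much it would alter the result depends on the cervical-to-vaginal ratio and on the variability, neither of which the documents give; the 79%, 39% and 20% in step 2 assume a 1.5-fold ratio and a full 10 v 10. Visit 6 withholds vaginal and cervical sampling during menstruation, pregnancy or possible infection, so the female-tract group may be smaller.

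The site-and-sex point is supporting and narrower. It concerns how the result is labelled and how optional samples are handled, and it does not show that the test is unsound. The groups are also anatomical and not strictly men versus women: the study population counts trans females as women, yet under Visit 6 a trans woman without a vagina would have a rectal biopsy.

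**What to change.** 1. Before any concentration data are seen, reconcile Sections 4 and 18 so that the tissue named in the endpoint is the tissue tested, for doxycycline and bictegravir. Report the other female-tract tissue as secondary, and give bictegravir one status throughout.
2. Define the main tissue and swab tests with one record per person: rectal from participants without a vagina, female-tract from those with one. State that a trans woman without a vagina falls in the rectal group. Call the result a site-and-population comparison, and do not report it as a pure site or pure sex effect.
3. Keep women's optional rectal samples out of the main test.
4. For women with both biopsies, report the within-woman rectal/female-tract geometric mean ratio with a 95% CI, for tissue and for the paired swabs, as supportive estimation only.

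The cost is SAP wording and a few lines of analysis, with no added visit, specimen or participant. The drawback is in item 4: it describes self-selected women only, their number is unknown, and with few pairs the interval may be too wide to be informative.

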| Study Title | Multipurpose Prevention of Post-Exposure Prophylaxis Regimens (Combo-PEP) |
| Study Design | 
To determine tissue pharmacology of a single dose of doxycycline for STI PEP, investigators at Emory University will collaborate with the Centers for Disease Control and Prevention (CDC) to conduct a clinical trial of up to 20 MSM and women aged 18-59, with measurement of anti-retroviral drug and doxycycline concentrations in the rectum and vaginal regions.
 
Study staff will plan to enroll participants who are HIV negative, at low risk for HIV and are not currently (or have no current plans) taking Post Exposure Prophylaxis (PEP) or Pre- Exposure Prophylaxis (PrEP). Enrolled participants will take a single dose of doxycycline (200mg) and Biktarvy® (200mg).
 
Biological specimens will be collected at 10 time points during this study. Study staff will recruit participants through existing research databases at the Hope Clinic and the Rollins School of Public Health, Research Match, and Clinical Data Warehouse. Internet and paper advertisements and community venues will also be used. At the first study visit, eligibility will be determined and screening blood work (approximately 14 mL), including an HIV test, will be performed. Participants will receive study drug in clinic and will provide documentation of taking doses (doxycycline and Biktarvy®) of the drug at home. During all study visits, participants will undergo blood collection (approximately 14 mL or 3 teaspoons of blood will be obtained), a urine sample, and collection of vaginal and rectal secretions. At certain visits, a vaginal and cervical biopsy will be performed on women, and a rectal biopsy will be performed on men, in addition to swab procedures. Women will have the option to do a rectal biopsy, as well. A pregnancy test will be done on women of childbearing potential at their screening and biopsy visit.
 |
| Primary Objective | To determine tissue pharmacology of single dose doxycycline for STI PEP |
| Secondary Objective(s) | To determine the tissue pharmacology of single dose bictegravir for HIV PEP. |

| | |
|---|---|
| Research Intervention(s)/Interactions | Doxycycline (200mg) and Biktarvy® (200mg) one combined dose |

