| Study Population | The population to be studied in this protocol are healthy HIV negative men who have sex with men (MSM) and HIV negative women (to include cisgender and trans females) at risk of HIV infection, who currently do not desire daily PrEP and are willing to undergo study procedures. |
| Sample Size | 20 participants (10 women & 10 MSM). |
| Study Duration for individual participants | The duration of this study is 2 years. Participants will be considered 'on study' for no more than 8 weeks. |
| Study Specific Abbreviations/ Definitions | MSM—Men who have sex with men STI—sexually transmitted infection PrEP—Pre- exposure prophylaxis TAF—tenofovir alafenamide FTC—emtricitabine TDF—tenofovir disoproxil fumarate HIV—Human Immunodeficiency Virus PEP—post-exposure prophylaxis CRAI—condomless receptive anal intercourse DOX—doxycycline BIC—bictegravir CDC—Centers for Disease Control and Prevention WHO—World Health Organization ARV—antiretroviral ED-PrEP—event-driven pre-exposure prophylaxis |
| Funding Source (if any) | Centers for Disease Control and Prevention |

2. Objectives

The purpose of this study is to determine the ability of doxycycline (200mg) and Biktarvy® (200mg) to penetrate mucosal tissues following a single oral dose and retain protective drug levels for extended periods of time.

Public Health Relevance: Event-driven PrEP (ED-PrEP) has been shown to be an effective solution for those who struggle to take a daily regimen of PrEP to prevent HIV; however, biomedical interventions for STI prevention have shown to be effective but have yet to be approved for use. There is limited data on the ability of DOX combined with ARVs to penetrate the mucosal tissues and provide protection against infection. Data regarding mucosal drug exposure will help inform development of multi-purpose event-driven dosing strategies.

Goal: The goal of this study is to understand the distribution of drug within mucosal tissues following a single oral dose of doxycycline and Biktarvy®.

3. Background

Sexually transmitted infections have been proven to increase the risk of HIV infection in men and women. Both men who have sex with men (MSM) and women continue to be disproportionately

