- 4) Intent to use HIV antiretroviral pre/post-exposure prophylaxis (PrEP or PEP) during the study, outside of the study procedures
- 5) Intent to use doxycycline or other tetracycline-derived antibiotics during the course of the study, outside of the study procedures
- 6) Any other clinical condition or prior therapy that, in the opinion of the investigator, would make the patient unsuitable for the study or unable to comply with the study requirements
- 7) Not pregnant and no plans on getting pregnant throughout the duration of the study
- 8) Known allergic reaction to study drugs.
- 9) Significant laboratory abnormalities at baseline visit for rectal biopsies, including but not limited to: a) Hgb ≤ 10 g/dL b) PTT > 1.5x ULN or INR > 1.5x ULN c) Platelet count <100,000

This study will not include any of the vulnerable populations listed below.

- Adults unable to consent
- Individuals who are not yet adults (infants, children, teenagers)
- Pregnant women
- Prisoners

11. Vulnerable Populations

This research will not involve human fetuses, neonates, prisoners, minors or cognitively impaired adults.

12. Local Number of Participants

This study will enroll a total of 20 participants (10 MSM and 10 women) at Emory. In order to enroll all 20 participants, it is anticipated that 40 will sign consent and be screened.

13. Recruitment Methods

[name] and co-investigators have a successful track record in recruiting MSM for their research protocols utilizing all of the recruitment methods detailed below. All recruitment materials will be IRB-approved prior to use.

Databases

The Hope Clinic maintains a large database of people who have previously expressed interest in participating in future research. Additionally, the study team will use existing Emory University databases, including Research Match and the Emory Healthcare Clinical Data Warehouse, who have consented to be contacted about research opportunities.

Email blasts and phone calls will be made to potential participants from these databases.

Face- to-face Engagements

Participants may be actively or passively recruited at community venues listed below and engaged with limited information about the study and study qualifications. A site contact sheet or a tablet using SurveyGizmo will be used to populate name, phone number, and email address of interested participants. Examples of locations used for face-to-face engagement are listed below:

- a. Community annual events attended by study population

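### The primary 24-hour doxycycline comparisons are read only through a Wilcoxon P<0.05; with about 10 people a side and no ratio or confidence interval, a non-significant result cannot be told apart from similar drug levels

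*Combined protocol and SAP*

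**What the plan says.** The summary table gives the primary objective as "To determine tissue pharmacology of single dose doxycycline for STI PEP". Section 2 (Objectives) puts the aim in terms of drug distribution in mucosal tissue and says that the data should inform event-driven dosing.

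Section 18 (Statistical Analysis Plan, Primary Outcomes) sets three doxycycline comparisons at 24 hours:

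- Plasma: "Plasma doxycycline concentrations at 24 hours will be compared between men and women using a Wilcoxon test".
- Swabs: "Median rectal and vaginal swab doxycycline concentrations collected at 24 hours after dosing will be compared using a Wilcoxon test".
- Tissue: "Median rectal and cervical tissues doxycycline concentrations collected at 24 hours after dosing will be compared using a Wilcoxon test".

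The only guidance on reading the results is "P-values less than 0.05 will be considered significant". The SAP names medians as what is compared. It does not commit to reporting them with a measure of spread, a between-site ratio or an interval, and no other section does so.

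Section 12 gives the size: "This study will enroll a total of 20 participants (10 MSM and 10 women) at Emory". No power, SD, target difference or other basis for that number is stated.

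Section 4 defines the endpoint differently from the SAP's tissue comparison: "Primary Endpoint: to compare doxycycline concentrations in rectal and vaginal biopsies collected 24 hours after a single dose".

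**The concern.** The objective asks how much drug reaches each site. A rank-test P value does not say how much, and in a study of 20 people it says little when it is not small. As written, the plan yields a significance verdict for each matrix and nothing that shows how large a difference the data allow.

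At stake is how a non-significant result can be used. If rectal and female genital tract concentrations give P=0.2, the planned output cannot show whether the two sites are within, say, 20% of each other or whether a twofold or threefold difference remains possible. A significant result would likewise come without a size. Either way, the information that dosing work needs would be in the data but not in the planned analysis.

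**Working it through.** **Plan's own figure.** The documents contain no power or precision calculation, so there is nothing to reproduce.

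**Inputs from the documents.** Ten per group (section 12), a Wilcoxon test and a 0.05 threshold (section 18).

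**Assumptions.** Two-sided rank-sum test on independent groups (the SAP states neither the variant nor the sidedness); log-normal concentrations with the same CV at both sites; CV from 40% to 120%; a true ratio of 2 as an illustration. None of the last three is in the documents.

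**Step 1: the test at 10 v 10.** From the exact null distribution, two-sided P<0.05 requires U≤23 or U≥77. The actual size is 0.0433.

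**Step 2: CV to log scale.** SD of log concentration = √ln(1+CV²). At CV 80%: √ln(1.64) = 0.703. The shift for a twofold ratio is ln 2 = 0.693.

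**Step 3: power and precision.** Power is simulated (40,000 to 60,000 trials per row). The interval factor for a geometric mean ratio is exp(t × SD × √(1/10+1/10)) with t = 2.101 on 18 df. At CV 80%: exp(2.101 × 0.703 × 0.447) = 1.94. The Hodges-Lehmann ratio is the exponentiated median of the 100 pairwise log differences. Its limits are the 24th smallest and 24th largest, with coverage 1 − 0.0433 = 95.7% (20,000 trials per row).

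| Assumed CV | Log-SD | Power, twofold | Missed | Geometric mean ratio: CI is estimate ÷ and × | Typical Hodges-Lehmann CI, true ratio 2 | CI contains 2 when test is non-significant |
|---|---|---|---|---|---|---|
| 40% | 0.385 | 95% | 5% | 1.44 | 1.37 to 2.93 | 77% |
| 50% | 0.472 | 84% | 16% | 1.56 | 1.26 to 3.18 | 89% |
| 60% | 0.555 | 71% | 29% | 1.68 | 1.16 to 3.45 | 93% |
| 80% | 0.703 | 50% | 50% | 1.94 | 1.0 to 4.0 | 96% |
| 100% | 0.833 | 38% | 62% | 2.19 | 0.89 to 4.55 | 97% |
| 120% | 0.944 | 30% | 70% | 2.43 | 0.79 to 5.09 | 97% |

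Power drops below 80% once the log-SD passes about 0.50 (CV about 53%). The ratio detectable with 80% power is about 2.05 at log-SD 0.5, 2.7 at 0.7 and 4.1 at 1.0.

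**Step 4: fewer tissue samples.** Ten per group is planned enrolment, not a tissue count. Under Visit 6 in section 6, female biopsies are withheld for menstruation, pregnancy or possible infection. The study population also counts trans women among the women, and Visit 6 gives anyone without a vagina a rectal biopsy. With 8 v 8 usable samples, power for a twofold ratio is 75%, 43% and 33% at CV 50%, 80% and 100%.

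**Reading the last column.** When the true ratio is 2 and the test misses it, the interval still includes 2 in 77% to 97% of trials. The interval would therefore usually show the result to be inconclusive. The P value alone would not.

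**The case against.** A rank test is a reasonable choice for skewed concentrations in small groups. A t test on log values gains little: about 83%, 44% and 31% power at log-SD 0.5, 0.8 and 1.0, against about 80%, 40% and 28% for the Wilcoxon test. The investigators may also report medians and ranges as a matter of course, and the SAP nowhere says that P≥0.05 means equal penetration. All of this stands. It means that the test is not at fault and that misuse of a null result is a risk, not something the plan states. It does not supply the missing estimate.

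Three stronger readings are tempting, and the documents do not support them.

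- A reader might infer that a real twofold difference will often be missed. That depends on the CV, which is not given. It is fair from about 60% upwards, but not at 40% or 50%, where power is 95% and 84%.
- A reader might infer that 20 is a miscalculated sample size. No calculation is stated, so none can be wrong.
- A reader might infer that the Wilcoxon test is invalid because up to 12 rectal biopsies are set against 1 to 2 cervical ones, giving unequal spread. The documents do not say that biopsies are averaged. If they were, with between- and within-person log-SD both 0.5, the SD ratio against one biopsy would be √[(0.25+0.25)/(0.25+0.25/12)] = 1.36. Simulated type I error at that ratio is 4.4%, and still 4.9% at a ratio of 2.

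**Conclusion.** The point holds as a gap in the planned output. Every primary doxycycline comparison rests on a P value, and no effect size or precision is planned for an objective that is about amount. That conclusion needs no assumed variance.

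The size of the risk does. For a true twofold ratio at 10 v 10, the chance of a non-significant result runs from about 5% (CV 40%) to about 70% (CV 120%), on the assumptions of log-normal data, equal spread, independent groups and a two-sided test. It is higher if female tissue samples are lost.

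This is a cheap improvement to what the trial can conclude, not an error in the test or in the sample size.

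**What to change.** 1. Reconcile the tissue first. Section 4 names vaginal biopsies and section 18 tests cervical tissue; state which is primary and whether the other is also compared.
2. Keep the Wilcoxon test and state that it is the two-sided rank-sum version. Say whether the optional rectal biopsies from women enter the rectal group, since a woman who gives both tissues would appear on both sides of the comparison.
3. For each 24-hour comparison, make the reported result the median or geometric mean at each site (or in each sex, for plasma) and the ratio between them with a 95% confidence interval. The Hodges-Lehmann estimate on log concentrations matches the Wilcoxon test; a geometric mean ratio is an alternative. Say how values below the assay limit are handled, because with many of them the pairwise ratios are not known.
4. Add one sentence: P≥0.05 is not evidence of similar levels, and the interval shows which ratios remain compatible with the data.

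The cost is a few sentences in the SAP and no new samples. The downside is that the intervals will be wide (at CV 80%, roughly half to twice the estimate), so some results will be seen to be inconclusive.
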